#### **6.4.3 Parameters to be monitored**

The following progress will be monitored throughout the course of the research to ensure the safety of subjects as well as the integrity and confidentiality of their data.

- An evaluation of the progress of the research study, including subject recruitment and retention, and an assessment of the timeliness and quality of the data.
- A review of collected data (including adverse events, unanticipated problems, and subject withdrawals) to determine whether there is a change to the anticipated benefit-to-risk assessment of study participation and whether the study should continue as originally designed, should be changed, or should be terminated.
- An assessment of external factors or relevant information (eg. pertinent scientific literature reports or therapeutic development, results of related studies) that may have an impact on the safety and study participants or the ethics of the research study.
- A review of study procedures designed to protect the privacy of the research subjects and the confidentiality of their research data.

The severity of adverse changes in physical signs or symptoms will be classified as follows:

- Grade 1 (Mild): asymptomatic or mild symptoms; clinical or diagnostic observation only; intervention not indicated.
- Grade 2 (Moderate): minimal, local or noninvasive intervention indicated; limiting age-appropriate ADL (Activities of Daily Living).
- Grade 3 (Severe): medically significant but not immediately life-threatening; hospitalization or prolongation of hospitalization indicated; disabling; limiting self care ADL.
- Grade 4 (Life-threatening): consequences; urgent intervention indicated.
- Grade 5 (Death): event is a direct cause of death.

#### **For AEs of Diarrhea:**

The severity of diarrhea will be graded according to the Common Terminology Criteria for Adverse Events (CTCAE) version 4.03:

- Grade 1: Increase of < 4 stools per day over baseline; mild increase in ostomy output compared with baseline
- Grade 2: Increase of 4 to 6 stools per day over baseline; moderate increase in ostomy output compared with baseline
- Grade 3: Increase of  $\geq$  7 stools per day over baseline; incontinence; hospitalization indicated; severe increase in ostomy output compared with baseline; limiting self-care activities of daily living
- Grade 4: Life-threatening consequences; urgent intervention indicated
- Grade 5: Death

#### **6.4.4 Frequency of Monitoring**

The Investigator will review subject safety data as it is generated. The Investigator, sub-investigators, and the research staff will meet on an approximately monthly interval to re-evaluate study goals, subject recruitment, data coding and retention, documentation and identification of adverse events, complaints and confidentiality of subjects. There will be an evaluation of the progress of the research study, including assessments of data quality, time lines, participant recruitment, accrual, and retention. The Investigator will also review the outcome and adverse event data to determine whether there is any change to the anticipated benefit-to-risk ratio of study participation and whether the study should continue as originally designed or should it be re-evaluated and changed.

The DSMB will also be expected to meet as needed, but not less than every six months to provide an overall summary status report to the regulatory agencies. [name] will not be involved in those monthly reviews.

#### **6.4.5 Reportable Adverse Events**

For this study, a serious adverse event is any untoward clinical event that is thought by either the investigator or the sponsor to be related to the study and results in any of the following outcomes: that is also:

- 1) Death
- 2) A life threatening adverse event
- 3) Inpatient hospitalization or prolongation of an existing hospitalization
- 4) A persistent or significant incapacity or substantial disruption of the ability to conduct normal life functions
- 5) A congenital anomaly or birth defect
- 6) Important medical events that may not result in death, be life threatening, or require
- 7) hospitalization may be considered serious when, based upon appropriate medical judgment, they may jeopardize the patient, or subject, and may require medical, or surgical intervention to prevent one of the serious outcomes listed above.

If clinically important and unexpected adverse experiences or clinically important study-related adverse experiences occur, they will be recorded on the adverse event case report form.

#### **6.4.6 Adverse Events Reporting Timeline**

Life-threatening or fatal unexpected adverse events associated with the use of the study drug or procedures must be reported to the IRB and Complexa Inc within 24 hours of discovery of the incident with subsequent follow-up submission of a detailed written report.

The FDA will be notified by telephone or facsimile transmission of a human adverse event that is fatal or life-threatening no later than 7 calendar days after receiving the respective human adverse event information, followed by the subsequent submission of a written IND Safety Report.

Serious and unexpected adverse events associated with the use of the study drug or procedures will be reported to the IRB and Complexa Inc. with subsequent follow-up submission of a detailed written report in accordance with the respective policies and procedures of the IRB. Written IND Safety Reports will be submitted to the FDA and Complexa Inc. as soon as possible and, in no event, later than 15 calendar days following the investigator-sponsor's receipt of the respective adverse event information.

The unexpected, life-threatening or fatal, suspected adverse reaction will be reported to the NHLBI within 7 calendar days. Unanticipated problems suggesting greater risk of harm to study participants than was previously known or recognized will be reported to NHLBI within 30 calendar days. Expedited SAE/UP reports to NHLBI will include the following elements:

- Study title, grant/contract number, PI name
- Description and date of the event or problem, including why it merits expedited reporting
- When available, date(s) when the event was reported to applicable governing bodies (e.g., IRB, FDA)
- Any corrective action planned or taken in response to the event or problem (e.g., study suspension, consent or protocol changes, additional training or security measures)

Communications from other applicable oversight bodies (eg: IRB, FDA, iDSMB, Complexa Inc.) regarding any applicable SAE/UP will also be reported to NHLBI.

#### **6.4.7 Reporting of Changes to Protocol and Consent**

Any amendments or modifications to the protocol will be shared with Complexa, Inc. Modifications to the clinical protocol or consent will also be submitted to the IRB for review prior to implementation of the changes in study practice. In the event that the study is suspended or terminated by the IRB or by the DSMB, or for other reasons, the NHLBI will be notified in writing including details as to the reasons for suspension or termination and any recommendations made by the IRB or DSMB. The FDA and Complexa, Inc. will also be notified of any changes to the protocol, suspensions or termination.

#### **6.4.8. Withdrawal of Subjects and Stopping Criteria:**

##### **STOPPING RULES:**

**Dose Reduction:** If subjects experience an increase of  $\geq 7$  stools/day over baseline or any serious AE believed to be possibly related to the study drug the dose of the study drug may be reduced to 150 mg/day or 75 mg/day at the discretion of the physician investigator. Subjects may be asked to return to the clinic for an unscheduled visit to assess their status if deemed necessary

based on the clinical judgement of the physician investigator. This unscheduled visit may require blood draws, vital signs and/or review of concomitant medication.

**Withdrawal of Subjects:** Subjects must be withdrawn from the study for the following reasons:

- Systolic BP < 80 mmHg
- Liver function test abnormalities: if ALT and/or AST > 8X ULN, the subject should stop taking study drug immediately. Medical evaluation should be undertaken as appropriate to the signs and symptoms manifested by the subject
- Positive pregnancy test

Subjects may be withdrawn from the study for the following reasons:

- At their own request
- At the specific request of the Investigator (eg: detection of a new significant safety concern related to the study drug)
- Occurrence of intercurrent diseases which in investigator's opinion, continuation of the study drug would be harmful to the subject's well-being
- Pertinent non-compliance with the conditions for the trial or instructions by the investigator
- Lost to follow up

Any subject removed from the study will remain under medical supervision until the condition is medically acceptable. Study subjects removed from the study will be replaced by enrolling another volunteer with similar demographics.

Subjects not completing the entire study should be fully evaluated when possible according to the following schedule:

- If study medication is discontinued on or prior to Week 4, complete all protocol required assessments scheduled for the End of Treatment visit excluding the RHC.
- If study medication is discontinued after Week 4 but prior to Week 10, complete all protocol required assessments scheduled for the End of Treatment visit excluding the RHC.
- If study medication is discontinued on or after Week 10 and prior to the start of the End of Treatment visit, complete all protocol required assessments scheduled for the End of Treatment Period.

All withdrawn subjects will be asked to report to the clinic for a follow-up visit (Visit 9).

**Discontinuation of the Clinical Trial:** For safety reasons, we may discontinue the study if the first two subjects enrolled experience any unexpected fatal or life-threatening events that can be attributed to the study drug; the study will be halted until data review by investigators and the iDSMB has rendered a final recommendation about study continuation.

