	
Potential subjects will undergo a screening visit to determine that eligibility requirements are met. Subjects who meet the inclusion criteria and none of the exclusion criteria will receive oral CXA-10 at the dose of 300 mg once daily for 12 weeks.
 
The first 10 subjects enrolled will receive the first dose of the study drug in the cardiac catheterization laboratory to evaluate acute pharmacological responses during the screening RHC (Visit1). This will be repeated at the end of the 12-week study RHC (Visit 7). Hemodynamic measures such as pulmonary vascular resistance (PVR), mean pulmonary artery pressure (mPAP) and left and right ventricular filling pressures, will be measured at baseline and 30 minutes post drug dose and CXA-10 metabolites will be measured with pharmacokinetics sampling time points at baseline and 2-6 hours post drug. Food will be given prior to dosing. Subjects will have 6-minute walk distance with Borg dyspnea scale assessments. Plasma NT-proBNP level, the World Health Organization (WHO) Functional Class assessment, and a health related quality of life questionnaire will also be collected. To evaluate in vivo insulin action in stimulating glucose disposal, oxidation, and nonoxidative disposal. An intravenous glucose tolerance test (IVGTT) will be performed before and after 12 weeks of CXA-10 treatment.
 
Subjects will be evaluated at 4-week intervals for occurrences of adverse events, laboratory test abnormalities, and evaluations of NT-proBNP plasma levels, six-minute walk distance with Borg dyspnea scale assessments, WHO functional classification and health related quality of life questionnaire recorded. Additional blood samples will be obtained for biomarkers and cytokines analysis, and physical activities will be monitored using a noninvasive accelerometer before and after study drug treatment.

Planned Sample Size:	27 completed subjects
Duration of Treatment:	12 weeks
Major Inclusion Criteria:	
 
• Male or female between 18-80 years of age inclusive at screening
 
• Weight <math>\geq</math> 40 kg or 88 lbs.
 
• Have a WHO Classification of Functional Status Class II or III
 
• Must meet all of the following hemodynamic criteria by means of a right heart catheterization: mPAP of <math>\geq</math>25 mmHg, PVR <math>\geq</math>
 

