## 2.5 STATISTICAL ANALYSIS

### 2.5.1 Sample Size Determination

We plan to enroll 30 subjects with PAH, allowing for a conservative drop-out rate of 10%, in this open label trial of oral CXA-10. We expect to see decrease in the PVR after 12 weeks of therapy. The intention to treat (ITT) population will consist of all subjects who have received at least one dose of study medication. To estimate our effect size for power calculations, we use data from the SUPER-1 sildenafil PAH trial (a randomized placebo control trial evaluating the effects of 20 mg, 40 mg or 80 mg TID of sildenafil in subjects with PH). Using the hemodynamic data from the 80 mg arm of the SUPER-1 trial and making a conservative assumption that our therapy will only have an effect that is 70% of sildenafil (decrease in PVR of 2.3 woods units with SD of 4.1), the sample size required for 80% power and P = 0.05 is 27 subjects (Table 2). We anticipate more than sufficient power to detect vasodilatory effects of NO2-OA administration (decreased PVR) after 3 months of therapy. Based on our extensive phase 1 data with CXA-10 formulations, we

anticipate the drug will cause no systemic blood pressure changes and no increases in methemoglobin levels.

**Table 2 Required sample size for different effect,  
Power =0.8 ,  $\alpha=0.05$ , two sided test**

% of Sildenafil	Mean (SD) PVR change, Woods unit	N
90	3.0 (4.9)	23
80	2.6 (4.2)	23
70	2.3 (4.1)	27

With safety as the primary outcome measure, we use Fleming's single stage phase II design with the following assumptions:  $\alpha = 0.05$ , Power= 0.80, lower proportion for rejection 70% (with no SAEs), higher proportion of acceptance 90% (with no SAEs) with maximum recruited patients of 27 patients resulting in a minimum number of success (with no SAEs to indicate that the treatment is safe) is 24. Thirty patients will be enrolled to compensate for up to 10% lost-to follow-up.

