### **3. HUMAN SUBJECTS**

The proposed study population will consist of 27 subjects with PAH. In order to achieve this number, it is anticipated that approximately 30 participants may need to be enrolled into this study to account for subjects who may not qualify the eligibility criteria or are withdrawn for any reasons.

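### The primary safety rule (24 of 27 free of an SAE) does not say who is counted and does not fit an enrollment of about 30 with replacement of removed subjects

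*Combined protocol and SAP*

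**What the plan says.** **The rule.** Section 2.5.1 takes safety as the primary outcome and uses a Fleming single-stage design: alpha 0.05, power 0.80, 70% SAE-free unacceptable, 90% acceptable. It is set up "with maximum recruited patients of 27 patients resulting in a minimum number of success" of 24.

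**Who the 27 are.** In that sentence they are the most to be recruited. The synopsis gives the planned sample size as "27 completed subjects", and section 2.1 also aims for at least 27 completers.

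**How many enter.** Sections 2.1, 2.5.1 and 3 all put enrollment at 30 or about 30, but for different reasons. Section 2.5.1 says: "Thirty patients will be enrolled to compensate for up to 10% lost-to follow-up". Section 3 says the extra places cover "subjects who may not qualify the eligibility criteria or are withdrawn for any reasons".

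**Replacement.** Section 6.4.8 says: "Study subjects removed from the study will be replaced by enrolling another volunteer with similar demographics". It sets no limit and does not say whether the removed subject's SAE still counts.

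**Analysis set.** The only set defined is in the PVR paragraph of section 2.5.1: "The intention to treat (ITT) population will consist of all subjects who have received at least one dose of study medication". Neither the SAE rule nor section 2.5.2 refers to it.

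**The concern.** A single-stage rule is one cut-off for one denominator. Here the cut-off is fixed at 24 for 27 subjects, while the plan brings in about 30 and replaces those removed. At least two readings are open: count 27 completers, or count everyone dosed. Section 2.5.1 gives a cut-off for 27 only, so the all-dosed reading has none once more than 27 are dosed.

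The choice matters because removal can be linked to harm. Section 6.4.2 foresees discontinuing a participant because of an SAE, and section 6.4.8 allows withdrawal over a new drug-related safety concern. On the completer reading, a subject who counts against the drug can give way to one who does not. What is at stake is the verdict on the primary outcome, and whether the stated alpha of 0.05 holds.

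**Working it through.** **Inputs.** From section 2.5.1: p0 = 0.70, p1 = 0.90, n = 27, cut-off 24, alpha 0.05 (taken as one-sided, since the side is not stated), power 0.80, enrollment 30. Allowance for loss: 27/0.9 = 30, which agrees with the plan.

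**Formula.** With X the number free of an SAE among n counted, X ~ Binomial(n, p). Alpha = P(X ≥ r | p = 0.70) and power = P(X ≥ r | p = 0.90).

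**Step 1: the plan's own rule, 24 of 27.**
- Alpha: the terms for 24, 25, 26 and 27 are 0.01513 + 0.00424 + 0.00076 + 0.00007 = 0.020.
- A cut-off of 23 would give 0.059, so 24 is indeed the smallest cut-off that keeps alpha at or below 0.05.
- Power: 0.2333 + 0.2520 + 0.1744 + 0.0581 = 0.718. The stated 0.80 is not reached.

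**Step 2: one data set, two counts.** Suppose 30 are dosed and 6 have an SAE; 3 of the 6 are removed and replaced, and the other 3 complete.
- Completers: 27 counted, 27 − 3 = 24 SAE-free. The rule passes, p = P(X ≥ 24 | 27, 0.70) = 0.020.
- All dosed: 30 counted, 30 − 6 = 24 SAE-free, p = P(X ≥ 24 | 30, 0.70) = 0.160. A cut-off of 25 gives 0.077 and 26 gives 0.030, so 26 are needed and the result fails.
- Keeping the cut-off at 24 while counting all 30 would make alpha 0.160.

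**Step 3: if removed SAE subjects left the count.** Assume a share s of SAE subjects is removed and not counted. At p0, each dosed subject is then a counted success with probability 0.70, a counted failure with 0.30(1 − s), or uncounted with 0.30s. Dosing stops at 27 counted or 30 dosed, and 24 successes are required. Exact enumeration gives:

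| Share s (assumed) | Chance of passing at 70% SAE-free |
|---|---|
| 0 | 0.020 |
| 10% | 0.034 |
| 17% | 0.048 |
| 18% | 0.050 |
| 25% | 0.067 |
| 50% | 0.126 |

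The 0.05 line is crossed at about 18%.

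**Step 4: cut-offs that follow the number dosed** (smallest r with alpha at or below 0.05):

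| Dosed | Cut-off | Alpha | Power |
|---|---|---|---|
| 27 | 24 | 0.020 | 0.718 |
| 28 | 24 | 0.047 | 0.858 |
| 29 | 25 | 0.038 | 0.842 |
| 30 | 26 | 0.030 | 0.825 |
| 31 | 27 | 0.024 | 0.807 |
| 32 | 28 | 0.019 | 0.789 |
| 33 | 28 | 0.041 | 0.894 |

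**The case against.** **Removal after an SAE may be rare.** An SAE is not itself a listed reason for withdrawal in section 6.4.8. For a serious event possibly related to the drug, that section mentions an optional dose reduction, and removal is at discretion. Section 6.4.5 also confines SAEs to events thought related to the study. This stands: a 10% share breaches nothing. It limits the likely size of the problem, but does not settle who is counted.

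**A reader might infer that the protocol drops SAE subjects from the safety count, or that the rule's alpha is inflated.** The documents support neither. They do not say such a subject leaves, and they do not say the subject stays. Without a cap on enrollment, Step 3 would give 0.077 at 25% and 0.273 at 50%, but that means dosing beyond the planned 30 or so.

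**Enrolled is not dosed.** Correct: that about 30 are dosed is an inference, since section 3 lets the 30 include subjects who do not qualify. That is a reason to tie the cut-off to the number actually dosed. The 27 recruited and 27 completed can be read as loose wording for one target, but loose wording in the denominator of a decision rule still needs repair.

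**Counting all dosed can err the other way.** With 23 of 27 completers SAE-free plus 3 early leavers without an SAE, the all-dosed count is 26 of 30 and passes, while 23 of 27 fails. Those three count as successes on little exposure. The first 10 subjects also receive a dose at the screening catheterization, so someone dosed once who then proves ineligible would enter the set. Both points stand, and the fix has to deal with them.

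**Conclusion.** The safety rule is not matched to the planned enrollment or to replacement, and its analysis set is not named. The same data can pass at 24 of 27 (p 0.020) and fail at 24 of 30 (p 0.160, 26 needed). That conclusion needs only the plan's own figures and an example allowed by its text. The alpha figures under replacement rest on assumed removal shares with dosing capped at 30, and exceed 0.05 only from about 18%. The power shortfall of 24 of 27 (0.718 against 0.80) is exact and needs no such assumption. The point should be settled before data are reviewed.

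A reader might extend this to PVR, because subjects who stop before Week 10 have no end-of-treatment catheterization, and infer a biased efficacy result. The documents do not support that: they show no link between stopping and the course of PVR, and neither size nor direction of bias can be derived. Section 2.5.5 already plans multiple imputation as a sensitivity analysis, records reasons for drop-out and compares completers with non-completers. Labelling the paired test as covering subjects with both catheterizations, and specifying the imputation, would be useful clarifications but are not part of this point.

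**What to change.** 1. In section 2.5.1, apply the SAE rule to every dosed subject. State in sections 2.5.1 and 6.4.8 that a replacement adds a subject and never removes one from the count.
2. Replace the single cut-off by the Step 4 table, read at the number actually dosed. Disclose that 24 of 27 has exact power 0.718 and that 28 of 32 (0.789) is also just below 0.80.
3. State the SAE counting window: Week 12, Visit 9, or the optional 6-month extension. Visit 9 is an off-drug follow-up for some subjects and the month 1 visit on drug for those in the extension, so the choice affects comparability.
4. Add a sensitivity count in which early leavers without an SAE are not successes. In the example above this gives 26 − 3 = 23 of 30, below 26. Say whether a subject dosed only at the screening catheterization is in the set.
5. Reconcile the 27 recruited of section 2.5.1 with the 27 completed of the synopsis, and the two reasons given for enrolling 30.

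The cost is a little SAP wording and a stricter count, with no extra visit or procedure. Section 6.4.2 already follows subjects discontinued for an SAE, and section 6.4.8 asks all withdrawn subjects to attend Visit 9.

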#### **6.4.2 Data Safety Monitoring Plan**

Before the start of the study, the DSMB will review the protocol for any major concern and the plans for data and safety monitoring to ensure that the frequency of monitoring is appropriate for the intervention.

Once the study is implemented, the DSMB will convene as often as necessary, but not less than every 6 months, to examine the accumulated safety and enrollment data, review study progress, and discuss other factors (internal or external to the study) that might impact continuation of the study as designed. A DSMB meeting may be requested by DSMB members, the PO, IRB, or study PI at any time to discuss safety concerns. Meetings may be held by conference calls or videoconferences or as face-to-face meetings.

During the study, the DSMB will review cumulative study data to evaluate safety, study conduct, and scientific validity and integrity of the trial as well as to assess the performance of overall study operations and any other relevant issues, as necessary. The DSMB will conclude each review with their recommendations to NHLBI, IRB and other applicable oversight bodies as to whether the study should continue without change, be modified, or terminated.

The study PI will ensure that the DSMB is apprised of all new safety information relevant to the study product and the study, including all protocol revisions, summary safety and enrollment data and all safety reports.

The IND Sponsor- will also submit annually an Annual Report to the FDA. The detailed written summary will be provided to the DSMB and the IRB. In addition, the DSMB Report will be submitted to the IRB at the time of continuing review annually or more often as required.

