Monitoring of safety and data quality in the proposed study will be the responsibility of all personnel on the project, with primary responsibility and supervision by the Investigator. The Institutional Review Board will approve the Statement of Informed Consent for the study and provide institutional oversight of data and safety issues. The study protocol will be approved prior to recruiting or obtaining consent from any participants. Moreover, the study will be reviewed at a minimum of annual basis (or more frequently as deemed necessary) by the IRB committee. Each participant will sign the Informed Consent Form described above prior to participating in the study. To ensure participant safety, once participants are enrolled in the study, study staff will immediately report all adverse and serious adverse events to one of the Investigators. The Investigator will, per standardized procedures, report them to the IRB for their review. These events should also be communicated to the sponsor of the IND. With regard to monitoring of data quality and protected health information, all required personnel proposed for this project will have the required human subjects and confidentiality training, which includes information about maintaining data integrity and security. Confidentiality will be guarded using established procedures such as storing data in locked cabinets within locked offices or locked data rooms, coding by study identification numbers rather than any personally identifying information to avoid revealing the identity of subjects, and aggregating data across participants. The key linking names and study identification numbers will be kept separately from the data sets with limited access by study personnel. Only study personnel will have access to the data sets on protected servers. Oversight of all aspects of data management will occur with the Investigator.

**Data Monitoring Plan.** The proposed study will use the FDA definition of adverse events (AE) and serious adverse events (SAE). Any SAE, which is unexpected and related to study intervention, will be reported immediately to the IRB and Complexa Inc., and will be followed by an additional

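### The only predefined trial-level halt with iDSMB review covers the first two subjects; after that, a pause and a DSMB review following the same event are discretionary

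*Combined protocol and SAP*

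**What the plan says.** Section 6.4.8, under discontinuation of the trial, says that the study may be discontinued "if the first two subjects enrolled experience any unexpected fatal or life-threatening events that can be attributed to the study drug", and that it will then be halted until the investigators and the iDSMB have reviewed the data and a recommendation has been made. The other items in 6.4.8 act on individual subjects: discretionary dose reduction, and withdrawal for low systolic pressure, raised transaminases or pregnancy.

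For every subject, including those after the second:

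- Section 6.4.2: "the DSMB will convene as often as necessary, but not less than every 6 months, to examine the accumulated safety and enrollment data". Also: "A DSMB meeting may be requested by DSMB members, the PO, IRB, or study PI at any time to discuss safety concerns". The PI must keep the board informed of new safety information and of all safety reports; no deadline is given. Staff pass adverse events to an investigator at once, who will "report them to the IRB for their review".
- Section 6.4.4: the investigator reviews safety data as they are generated, and the study team meets about monthly. The six-month minimum for the DSMB is repeated.
- Section 6.4.6: unexpected fatal or life-threatening events associated with the drug or procedures "must be reported to the IRB and Complexa Inc within 24 hours of discovery of the incident". The FDA and NHLBI are notified within 7 calendar days. The DSMB is not named as a recipient of these reports.
- Section 6.4.7 recognises that the IRB or the DSMB can suspend or terminate the study.

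**The concern.** Safety is the main objective and the primary endpoint. The sponsor has already judged that an unexpected, drug-attributed fatal or life-threatening event in the first two subjects warrants stopping until the iDSMB has advised. The protocol gives no reason why the same event in subject 3 should be handled differently. As written, the later event must be reported, but nothing obliges anyone to pause enrolment or dosing, or to convene the board.

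Two subjects offer little reassurance. Section 1.3.3 reports 7 FSGS patients treated for up to 90 days at 300 mg. The human studies described were in healthy, obese or renal-disease subjects, not in PAH.

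The existing sentence is also loose in two ways. It does not say whether an event in one of the two subjects is enough or both must have one, and it puts a permissive verb (may discontinue) beside a mandatory one (will be halted).

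**Working it through.** **1. The base of 28.** Section 2.5.1 gives 27 subjects and 10% loss: 27 / (1 - 0.10) = 30, which reproduces the planned enrolment. Outside the trigger: 30 - 2 = 28, and 28/30 = 93.3%. Enrolment is approximate and removed subjects are replaced (6.4.8), so the count could be higher.

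**2. Who must do what after such an event.**

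| Step | Subjects 1-2 | Subject 3 on |
|---|---|---|
| Report to IRB, supplier, FDA, NHLBI | Required (6.4.6) | Required (6.4.6) |
| PI informs DSMB | Required, no deadline (6.4.2) | Required, no deadline (6.4.2) |
| DSMB meets because of the event | Required (6.4.8) | Discretionary (6.4.2) |
| Study pauses | Required (6.4.8) | Discretionary (6.4.7) |

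The two columns differ only in the last two rows.

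**3. Where a qualifying event would fall.** The documents give no rate, so the per-subject risk p is an assumption. At least one event in n subjects: 1 - (1 - p)^n. Both of the first two: p^2. Share of trials with any event that have none in the first two: 1 - [1 - (1 - p)^2] / [1 - (1 - p)^30].

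| p | Subjects 1-2, at least one | Subjects 1-2, both | Subjects 3-30, at least one | No event in first two, given any in 30 |
|---|---|---|---|---|
| 1% | 2.0% | 0.01% | 24.5% | 92% |
| 2% | 4.0% | 0.04% | 43.2% | 91% |
| 3% | 5.9% | 0.09% | 57.4% | 90% |
| 5% | 9.8% | 0.25% | 76.2% | 88% |

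As a rough guide to p, Section 1.3.3 reports no SAEs in the oral Phase 1 studies (80 subjects in its diarrhea count) and no deaths or treatment-related SAEs in 18 + 7 = 25 FSGS patients. Zero in 80 + 25 = 105 gives an approximate 95% upper bound of 3/105 = 2.9%. These were not PAH patients, Phase 1 exposure was short, and the text does not say that all 80 received active drug. The 5% row is therefore pessimistic, though not excluded for PAH.

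**4. Worst-case delay.** Assumptions: evenly spaced enrolment of 30; one event in a random subject from 3 to 30, with onset uniform over 3 months; DSMB meetings exactly 6 months apart; and nobody calls an ad hoc meeting. The mean wait to the next meeting is about 3 months. Mean further enrolments before it, by simulation:

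| Assumed enrolments per month | No ad hoc meeting | Meeting within two weeks (taken as half a month) |
|---|---|---|
| 0.25 | 0.8 | - |
| 0.5 | 1.8 | - |
| 1 | 3.0 | 0.5 |
| 2 | 4.5 | 0.9 |
| 3 | 5.3 | 1.2 |

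Meetings are counted from first enrolment. If their dates are unrelated to enrolment, the no-meeting figures at 1, 2 and 3 per month are 2.6, 4.5 and 5.6.

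**The case against.** The strongest reply is that a strict rule for the first exposures, followed by standing DSMB discretion, is a legitimate design. The board must be told of every safety report, is to convene whenever needed, and can be called by its own members, the PI, the IRB or the program officer. A board told of an unexpected drug-attributed death would very probably meet at once. This largely stands: the difference is between an automatic response and a discretionary one, and the delays in the middle column of step 4 arise only if everyone entitled to call a meeting declines.

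A reader might infer that later subjects have no effective safety oversight, or that the trial cannot be stopped after subject 2. The documents do not support that. Section 6.4.7 speaks of what follows "In the event that the study is suspended or terminated by the IRB or by the DSMB", and reporting and review continue for every subject.

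A reader might also infer that the SAE criterion in Section 2.5.1 ("minimum number of success (with no SAEs to indicate that the treatment is safe) is 24") should trigger a review once a fourth subject has an SAE, since 27 - 24 + 1 = 4. That does not follow. The criterion belongs to a single-stage design assessed at the end, so having no interim boundary is not an omission. With 30 enrolled and removed subjects replaced, a fourth SAE need not put 24 of 27 out of reach. The review would also be called often for an acceptable drug: at a 10% SAE rate, the chance of at least four affected subjects is 28.2% among 27 and 35.3% among 30.

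**Conclusion.** The point holds as a gap in the rule's coverage. The only predefined halt with iDSMB review stops at the second subject. For about 28 of 30, the pause and the review after the same event are left to judgement. That reading rests on the text alone and is secure.

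The practical size is uncertain. Under assumed risks of 1% to 5%, roughly nine in ten trials with at least one qualifying event (88% to 92%) would have none in the first two subjects. If the trigger needs both subjects to have an event, it would almost never operate (0.01% to 0.25%). The further enrolments in step 4 are a ceiling under assumed accrual with no ad hoc meeting, not an expected number. With a prompt meeting they fall to about one or fewer. Neither the trial's validity nor its error rates are affected. This is a cheap improvement.

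**What to change.** Replace the discontinuation sentence in Section 6.4.8 with wording to this effect:

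> Should any enrolled subject have an unexpected event that is fatal or life-threatening and attributable to CXA-10, enrolment and dosing stop until the investigators and the iDSMB have reviewed the data and the iDSMB has recommended whether to continue. The study may then be discontinued.

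This keeps the sponsor's own narrow trigger, so expected PAH deterioration would not activate it. It settles that one subject is enough, and that the halt is mandatory while discontinuation is a later decision. Any enrolled subject includes those in the optional open-label extension.

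The cost is one sentence and a possible pause after subject 2. A pause in dosing would interrupt treatment for those partway through their 12 weeks: 84 days is about 2.8 months, so about 3, 6 and 8 subjects at the assumed 1, 2 and 3 enrolments per month, plus any in the extension. A short, stated target time for the iDSMB review would limit this. Sample size, endpoints and the end-of-trial safety criterion stay as they are.
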